Despite significant progress made in ABC technique, tumor and organ motion could only be minimized and not eliminated completely. Assessing patient specific tumor/organ motion (both intra- and interfractional) throughout the course of SBRT treatment offers the possibility of ensuring delivery of the prescribed target dose while simultaneously minimizing normal tissue damage. In order to monitor the abdominal soft tissue motion, the Department of Radiation Oncology has developed a 4D ultrasound technique based on an ultrasound probe holder and a continuous motion monitoring software.

The 4D ultrasound image is acquired by using a motorized 3D ultrasound probe and image continuously. 4D ultrasound is a new non-ionizing and non-invasive imaging technique that allows continuous image acquisitions for real-time motion monitoring during the radiation treatment. Ultrasound is a proven modality for soft tissue localization (ref-prostate-breast). Several studies  have shown that even with older version of ultrasound system, the ultrasound images correlates with CT images within a small absolute magnitude of difference (about 3 mm), therefore we expect to have good agreement between the reference CT simulation and reference 4D ultrasound. Ultrasound motion monitoring during treatment delivery is based on real-time automatic registration of ultrasound images acquired on treatment days to reference ultrasound images acquired at the beginning of treatment, thus removing any inter-modality tracking uncertainty and inter-user variability. The ultrasound probe in the CT image will be contoured and radiation beams that directly pass through the ultrasound probe will be avoided. An SBRT treatment plan usually consist of multiple (9 – 12 beams for IMRT technique) co-planar beams delivered around the isocenter placed inside the tumor. Omitting the small range of angle directly passing through the ultrasound probe will not compromise the treatment plan dosimetry quality.

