## **3. Background**

SBRT of the abdomen has been limited by the movement of intra-abdominal organs that naturally occurs with respiration and bowel movement. Currently at Johns Hopkins Hospital, breathing motion management is employed using ABC technique for patient treated with pancreas and liver SBRT if the tumor and/or abdominal organs move more than 3 mm during a breathing cycle. While ABC device has been reported to reduce respiratory motion to below 2 mm, small variation of breath-holds may lead to tumor displacement and suboptimal dose delivery. Assessing patient specific tumor/organ motion (both intra- and interfractional) throughout the course of SBRT treatment offers the possibility of ensuring accurate delivery of the prescribed target dose while simultaneously minimizing normal tissue damage. This can be achieved by using Clarity 3D ultrasound system together with ABC device for real-time tracking of the pancreas and liver during SBRT treatment.

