## **4. Study Procedures**

- a. **Arm 1:** Validate the ultrasound tracking and establish reference range of motion for abdominal soft tissue motion from healthy individuals.

Fifteen healthy volunteers will be enrolled and informed consent obtained per study guidelines as described. A reference ultrasound scan will be conducted on each subject during breath-hold. Subjects will be required to lie in supine position and engaged with ABC; an ultrasound probe will be placed at the abdomen area with minimal pressure applied. Continuous motion monitoring is achieved by acquiring 4D ultrasound images using a motorized 3D ultrasound probe to image the pancreas, liver and other intra-abdominal organs continuously. Several 4D ultrasound scans will be collected during subsequent breath-holds that serve as secondary images. Registration of the reference and secondary ultrasound scans will be performed with automated registration algorithm built-in with the ultrasound system to evaluate abdominal soft-tissues and organs motion. Additional registration of ultrasound images will be performed with Velocity software to evaluate accuracy of automated registration software in the ultrasound system.

- b. **Arm 2:** Monitor the abdominal soft tissue motion of pancreas patients treated with SBRT during the whole course of treatment.

Thirty pancreatic cancer patients receiving SBRT treatment with ABC will be enrolled and informed consent obtained per study guidelines as described. A 4D ultrasound scan will be acquired at the time at simulation and used as a reference ultrasound image for localizing

tracking target. The ultrasound probe will be placed at the abdominal area to monitor the pancreas motion. The probe will remain in place during the CT scan. Patient setup and the ultrasound probe location will be recorded so that the same setup can be reproduced during treatment delivery. The ultrasound probe in the CT image will be contoured and radiation beams that directly pass through the ultrasound probe will be avoided.

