On each treatment day, 4D ultrasound images will be acquired continuously during beam on time to monitor pancreas motion. The system will record all relevant images, but will not be used in clinical decision making. These data will be used to evaluate the magnitude of target motion and dosimetry deviation due to the motion. Intra-fraction CBCT images acquired during treatment will be registered with reference CT images. Organ motion registered by ultrasound will be compared to motion recorded by CBCT and the accuracy of the ultrasound system will be evaluated.

c. **Arm 3:** Monitor the abdominal soft tissue motion of liver patients receiving SBRT treatment with ABC during the whole course of treatment.

Twenty hepatic cancer patients being treated with SBRT treatment will be enrolled and informed consent obtained per study guidelines as described. A 4D ultrasound scan will be acquired at the time at simulation and used as a reference ultrasound image for localizing tracking target. The ultrasound probe will be placed at the abdominal area to monitor the liver motion. The probe will remain in place during the CT scan. Patient setup and the ultrasound probe location will be recorded so that the same setup could be reproduced during treatment delivery. The ultrasound probe in the CT image will be contoured and radiation beams that directly pass through the ultrasound probe will be avoided.

On each treatment day, 4D ultrasound images will be acquired continuously during beam on time to monitor liver motion. The system will record all relevant images, but will not be used in clinical decision making. These data will be used to evaluate the magnitude of target motion and dosimetry deviation due to the motion. Intra-fraction CBCT images acquired during treatment will be registered with reference CT images. Organ motion registered by ultrasound will be compared to motion recorded by CBCT and the accuracy of the ultrasound system will be evaluated.

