## 7. Study Statistics

a. Analytic plan for primary objectives:

An effective workflow for real time monitoring of abdominal soft-tissue due to respiration using a 4D ultrasound system will be developed through the use of healthy controls. As

described earlier, these controls will provide data for estimating the background reference for abdominal soft tissue. Data collected on controls will be summarized with descriptive statistics. Quantitative analysis of target/organ motion and displacement recorded in 4D real-time ultrasound scan will be carried out to assess both intra- and interfractional variation as described above in the study. This study will help us to ensure delivery of the prescribed target dose while simultaneously minimizing normal tissue damage. We will consider the approach feasible if we are able to successfully complete the procedure and output the associated data for 50% of the study participants. The software will output a motion curve over time. We will calculate the difference between values on the curve and the values from CBCT at the specific time points that CBCT is performed, and summarize the differences using descriptive statistics. A 95% confidence interval for the difference will be reported. These data will be used to evaluate the accuracy of the 4D ultrasound system.

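### Arms 2 and 3 do not tie the reference ultrasound and the reference CT to one breath-hold or measure any gap between them, so reference mismatch can be counted as ultrasound error

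*Combined protocol and SAP*

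**What the plan says.** In Arm 2 (section 4b), "A 4D ultrasound scan will be acquired at the time at simulation and used as a reference ultrasound image for localizing" the tracking target. Of the link to the CT it says only "The probe will remain in place during the CT scan". Section 4c describes the same procedure for liver patients. The Arm 1 text is more specific about breathing state: "A reference ultrasound scan will be conducted on each subject during breath-hold". Arms 2 and 3 have no matching sentence.

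The two motion measures have different zero points. For ultrasound, the Abstract describes "real-time automatic registration of ultrasound images acquired on treatment days to reference ultrasound images acquired at the beginning of treatment". For CBCT, sections 4b and 4c state "Intra-fraction CBCT images acquired during treatment will be registered with reference CT images". The Abstract therefore places the reference ultrasound at the start of treatment, while section 4 places it at simulation.

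The accuracy analysis in section 7a is: "We will calculate the difference between values on the curve and the values from CBCT at the specific time points that CBCT is performed". These differences get descriptive statistics and a 95% confidence interval, and are then used to judge the ultrasound system. Section 7a mentions no re-zeroing, no check of the two references against each other and no patient-level term. On whether the references agree, the Abstract says "we expect to have good agreement between the reference CT simulation and reference 4D ultrasound". Section 3 acknowledges that "small variation of breath-holds may lead to tumor displacement and suboptimal dose delivery".

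**The concern.** A difference between two displacement measures shows tracking accuracy only if both start from the same organ position. Here one starts from the reference ultrasound and the other from the reference CT. The plan expects these to agree but has no step that makes them agree or shows whether they do, and its own background section says breath-holds vary.

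These differences are the planned evidence for primary objective (c), the accuracy of ultrasound against CBCT. If the two references were taken at different breath-hold levels, part of the reported disagreement would come from how the simulation scans were acquired and not from how well the system follows the organ. Without ultrasound recorded during the CT, that part cannot be recovered later.

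**Working it through.** The plan has no figure to reproduce: section 7c fixes enrolment at 30 pancreatic and 20 hepatic patients and says the variability is unknown.

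**Step 1, the identity.** Let x be organ position and e measurement error.

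- Ultrasound at time t: x(t) − x(US ref) + e_US
- CBCT at time t: x(t) − x(CT ref) + e_CBCT
- Difference: [x(CT ref) − x(US ref)] + e_US − e_CBCT

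The bracket does not depend on t. It is the same at every CBCT of a patient for whom these two references are used throughout, and it is zero only if both references caught the organ in the same position.

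**Step 2, size of the bracket.** Assume the references come from two separate breath-holds whose levels vary independently with SD s. The offset SD is then √2·s. For s = 0.5 and 1.0 mm (assumed), this is 0.71 and 1.41 mm.

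**Step 3, effect on the spread.** Let τ be the SD of e_US − e_CBCT, called tracking SD here (assumed; the documents give none). The SD of the differences is √(τ² + 2s²), and the half-width of the 95% limits of agreement is 1.96 times that.

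| τ (mm) | SD, s = 0.5 | SD, s = 1.0 | Inflation over τ | Limits without offset | Limits with offset |
|---|---|---|---|---|---|
| 1 | √1.5 = 1.22 | √3 = 1.73 | 22-73% | ±1.96 | ±2.40 to ±3.39 |
| 2 | √4.5 = 2.12 | √6 = 2.45 | 6-22% | ±3.92 | ±4.16 to ±4.80 |
| 3 | √9.5 = 3.08 | √11 = 3.32 | 3-11% | ±5.88 | ±6.04 to ±6.50 |

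Section 3 reports residual respiratory motion under ABC below 2 mm. That is not a between-hold SD. Read as a uniform spread with a total range of 2 mm, it gives s = 2/√12 = 0.58; read as ±2 mm, it gives s = 4/√12 = 1.15. With τ = 1 mm, the SD of the differences is then 1.29 or 1.92 mm, so the assumed range for s is of a plausible order.

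**Step 4, effect on the arm mean.** If the mismatch is random, the offset averages zero, so the expected mean difference is unchanged (simulated bias below 0.005 mm). The chance contribution to an arm mean has a 95% half-width of 1.96·√2·s/√n. For s = 0.58 to 1.15 this is 0.29 to 0.58 mm with n = 30 and 0.36 to 0.72 mm with n = 20. It shrinks with more patients and not with more CBCTs per patient.

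**Step 5, the confidence interval.** Section 7a does not say whether the unit is the CBCT time point or the patient. In 20,000 simulated runs with 5 CBCT points per patient and τ = 1 mm (both assumed), an interval treating all points as independent covered about 77% at s = 0.58 and about 66% at s = 1.15, not 95%. An interval based on patient means covered 95%.

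**The case against.** The plan is silent; it does not say that the references come from different breath-holds. The probe is on the patient during the CT, so acquisition in the same breath-hold is possible and may be what the team intends. **This stands:** the offset is a possibility that the plan leaves open. A reader might infer that every patient's differences do carry an offset, but the documents do not establish that.

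The missing breath-hold sentence in Arms 2 and 3 is weak evidence by itself. Both arms are described as treated with ABC, which is a breath-hold technique, so breath-hold acquisition is strongly implied. **This also stands.** The gap is that the same breath-hold is not required.

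If both measures were re-zeroed at each fraction, the offset would cancel. That is true, but section 7a does not say so and section 4 registers CBCT to the reference CT.

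A reader might also infer that the ultrasound will look biased on average. Random mismatch does not do that; it adds between-patient spread. There is no accuracy threshold, the data are called pilot data and the ultrasound does not guide treatment, so no pass/fail conclusion changes. These points limit the consequence, but a reported spread and interval can still be misread.

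Finally, a mismatch with the planning CT could be regarded as part of the system's end-to-end error. That is a legitimate target, but the plan does not say that it is the intended one. Reporting the components separately serves both readings.

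**Conclusion.** The point holds in conditional form. The plan does not require the two references in Arms 2 and 3 to share a breath-hold, does not measure the gap between them and contradicts itself on when the reference ultrasound is taken. If the organ positions differ, a patient-specific constant is counted as ultrasound error.

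The size cannot be derived from the documents. It rests on an assumed s of 0.5 to 1.0 mm, independent breath-hold levels and an assumed tracking SD. Quoting 22-73% alone would be tempting, but that range needs a tracking SD of 1 mm, which nothing in the documents supports. At 3 mm the inflation is only 3-11%. The full range should be given.

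This should be changed, because it concerns the evidence for a primary objective and the missing simulation recording cannot be recreated. Confidence is medium, because actual practice at simulation may already meet the requirement.

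**What to change.** **Abstract and section 4.** Reconcile the two statements of when the reference ultrasound is acquired. A reference taken at the start of treatment could not share the planning-CT breath-hold, and the recording below would then be needed to link the two.

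**Sections 4b and 4c.** Add: *Ultrasound is recorded through the planning-CT breath-hold, and the reference volume is taken from that recording.* Add rules for departures:

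- If the reference volume comes from another breath-hold but ultrasound was recorded during the CT, register that recording to the reference volume and subtract the measured displacement from the patient's ultrasound values.
- If there was no recording during the CT, nothing can be subtracted. Flag the patient and report the differences with and without such patients.

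**Section 7a.** State whether either measure is re-zeroed at each fraction. Analyse the differences with a patient-level term, for example a random intercept, and base the 95% confidence interval on it. Report between-patient and within-patient components. Do not label the patient mean as pure reference offset: it can also contain real patient-specific ultrasound or CBCT registration bias, and removing it from tracking error could flatter the system.

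**Cost.** A few sentences, a small extra step at simulation and slightly more analysis. The probe is already in place during the CT, so no scan or visit is added. This assumes that the probe can image while the CT is acquired, which section 4 does not state and the team should confirm.

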### Secondary objective:

- a. Evaluation of dosimetry differences due to target/organ motion observed

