**b. Analytical plan for secondary objectives:**

Quantitative analysis dosimetry deviation due to patient specific tumor/organ motion (both intra- and interfractional) throughout the course of SBRT treatment will be carried out. The actual dose received will be compared to the intended dose, and their difference will be summarized with descriptive statistics.

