**8. Risks**

- a. Medical risks: None; data will be acquired but there will be no change in the radiation therapy intervention.
- b. Legal risks such as the risks that would be associated with breach of confidentiality: While data will be stored data in secure locked files (computer files will be password protected and any paper records will be stored in the research office at Johns Hopkins under lock and key) in which only the research team has access, there is always the risk that confidentiality will be lost
- c. Financial risks to the participants: None

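### Section 8a gives medical risk as none because radiation therapy is unchanged, but Section 4 makes planning in Arms 2 and 3 avoid beams through a research-only probe

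*Combined protocol and SAP*

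**What the plan says.** In Section 4, patients in Arms 2 and 3 have the probe placed on the abdomen at simulation. It stays there for the CT, and ultrasound is acquired while the beam is on at each treatment. The planning instruction is the same for both arms: "The ultrasound probe in the CT image will be contoured and radiation beams that directly pass through the ultrasound probe will be avoided". Section 4 also says that the ultrasound system records images but does not inform clinical decisions.

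Section 8a reads: "Medical risks: None; data will be acquired but there will be no change in the radiation therapy intervention".

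The Abstract (Section 1) describes usual plans as having 9 to 12 co-planar IMRT beams and adds: "Omitting the small range of angle directly passing through the ultrasound probe will not compromise the treatment plan dosimetry quality".

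The only dose analysis serves the secondary objective in Section 2, "Evaluation of dosimetry differences due to target/organ motion observed". Section 7b carries it out: "The actual dose received will be compared to the intended dose, and their difference will be summarized with descriptive statistics".

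**The concern.** A risk section is where an ethics reviewer looks for what the research adds to routine care. Here it gives one reason for a risk of none, and the procedures contradict that reason. A device present only for research restricts the beam directions open to the planner, in patients who, by Section 9, gain nothing from taking part.

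Two things are at stake. A reader relying on Section 8 would not learn that planning is constrained. And the protocol does not say what happens if a probe-avoiding plan falls short on target coverage or organ dose.

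**Working it through.** The documents give no dose figure or limit on this point, so there is no stated number to reproduce. The check sets the sections side by side.

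1. **What 8a claims.** Medical risk is none, and the one reason offered is that the radiation therapy intervention does not change.

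2. **What Section 4 requires.** The probe is contoured on the planning CT and beams directly through it are avoided. The Abstract itself describes this as omitting a range of angles. The set of permitted beam directions is therefore smaller than it would be without the study.

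3. **Why the constraint exists.** The ultrasound output is not used clinically, so the patient's own treatment does not need the probe.

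4. **Who is affected.** Section 7c plans 30 pancreatic and 20 hepatic patients: 30 + 20 = 50 under the constraint. The 15 healthy volunteers in Arm 1 have no radiation treatment, so the point does not reach them.

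5. **Whether the Abstract reconciles the two.** Its assurance is that the omission does no harm. Section 8a says that there is no change. Even if the first is true, it does not make the second true. The assurance rests on the usual number of beams; no data, citation or acceptance limit comes with it.

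6. **Whether any stated analysis tests the assurance.** Write D_free for the dose of a plan made without the probe constraint, D_plan for the dose of the probe-avoiding plan, and D_actual for the dose received.
   - Section 7b estimates D_actual − D_plan, reading the intended dose as that of the treated plan. The term is not defined, but this is the natural reading under a motion objective.
   - The cost of avoidance is D_plan − D_free.
   - No section calls for a plan giving D_free, so the second difference is not available at any sample size.

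7. **Whether the size can be derived.** It would need the probe's width, its distance from the isocentre, the field size, the beam arrangement, and how far re-optimising the remaining beams recovers the plan. Only the usual range of 9 to 12 beams is given. The dose effect is unknown from these documents.

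**The case against.** The strongest reply is that nothing is hidden. The Abstract tells the same readers that angles are left out and gives the authors' judgement that quality does not suffer. Read with Section 4, 8a may mean only that the recorded data will not alter treatment. That is a fair account of what the authors probably meant, and it makes this a repair of wording rather than evidence of bad practice. It does not rescue the sentence, which speaks of the therapy and not of the use of the data.

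The clinic's own plan review is not in these documents and may already stop a plan that breaks a limit. That also stands. It is why a short acceptance rule is enough, and why the rule should cost little.

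A reader might infer more than the documents support:

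- *That patients receive a worse dose.* The number of beams cannot be turned into a dose penalty. The probe geometry is not given, angles may be replaced, and IMRT can re-optimise the rest.
- *That all 50 plans differ from what they would have been.* Fifty is the number planned under the constraint. In some patients no beam may have needed to move.
- *That Section 7b is faulty.* It is set to measure deviation due to motion. If nothing moves, zero is its correct answer. It makes no claim about the cost of avoiding the probe.
- *That probe placement at treatment is uncontrolled.* Section 4 says "Patient setup and the ultrasound probe location will be recorded so that the same setup can be reproduced during treatment delivery". How this is confirmed before beam-on is not written, but that is missing detail and not part of this point.
- *That patients are not told.* Consent pages are not available here, so this cannot be judged.

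**Conclusion.** The point holds in a limited form. The reason that 8a gives for no medical risk is wrong as written for Arms 2 and 3, because research use of the probe constrains treatment planning for the 50 planned patients. The assurance that this is harmless is unsupported in the documents and is not tested by any stated analysis.

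The contradiction rests on the text alone and needs no assumption about geometry or dose. The statement that no analysis tests the assurance assumes that the intended dose in 7b is that of the treated plan. The documents neither show harm nor allow its size to be bounded. The correction should be made because it bears on patient safety and is cheap.

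**What to change.** **1. Replace Section 8a with:**

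> The probe is in place during CT and beam-on, and beam angles through it are avoided in planning. This could change target coverage or normal-tissue dose. Ultrasound data will not be used to alter treatment.

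**2. Add to Section 4, Arms 2 and 3:**

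> The probe-avoiding plan must meet the clinic's usual target-coverage and organ-at-risk limits; if it does not, the patient is planned and treated without the probe and counts as not completed for the 7a feasibility criterion.

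The first change is a text edit. The second adds a check against limits that the clinic is assumed to apply already; the protocol should cite them.

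The cost of the second is that some patients, in a number the documents do not allow one to predict, may yield no ultrasound data. Section 7a calls the approach feasible if the team can "successfully complete the procedure and output the associated data for 50% of the study participants". Each patient treated without the probe lowers the completed share by 1/30 = 3.3 percentage points within Arm 2, 1/20 = 5.0 within Arm 3, or 1/50 = 2.0 across both. Counting such patients as not completed keeps the criterion honest about how often the probe cannot be used.

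The simulation CT is taken with the probe in place. The clinic should therefore say whether a plan without the probe can be made on that scan or needs another; the documents do not settle this.

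Comparison plans made without probe avoidance, on the same CT, would measure the cost of the constraint directly. They amount to an added planning study of up to 50 plans with unstated planner effort, so they are optional.
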